Dilatation (cm)	1	1-2	3-4	>4
Length of cervix (cm)	>4	2-4	1-2	<1
Station	-3	-2	-1	0
Consistency	Firm	Average	Soft	-

Position	Posterior	Mid/Anterior	-	-
----------	-----------	--------------	---	---

SELECTION AND WITHDRAWAL OF SUBJECTS

1. Sample population:
 - a. All pregnant women with one previous Caesarean section who are admitted to Sibug Hospital for IOL will be recruited in the study.
2. Inclusion criteria:
 - a. The inclusion criteria are age at least 18 years old, gestational age ≥ 37 weeks, singleton pregnancy, reassuring fetal status and modified Bishop score ≤ 6 .
3. Exclusion criteria:
 - a. Women with ruptured membranes, intrauterine death, polyhydramnios, severe fetal anomalies, multiple pregnancy.
 - b. Women with contraindications for IOL eg. placenta previa, suspected macrosomia, suspected cephalopelvic disproportion, non-cephalic presentation, and obstructive pelvic masses.
4. Sample size determination:
 - a. We had searched electronic databases including PubMed, Cochrane Library, Scopus, Ovid, JSTOR and Google Scholar. We found that there was no study comparing the two IOL methods, thus no prior information is available for sample size calculation.
 - b. Based on Julious SA (32), we will recruit 24 subjects (a sample size of 12 per group) first, then do an interim analysis and calculate the actual sample size required for a full RCT. The justifications for this interim sample size are based on rationale about feasibility, precision about the mean and variance, and regulatory considerations.
 - c. With α at 0.05 and power at 0.8, the final sample size will be calculated based on the study primary outcome of induction to delivery interval. As this outcome is a continuous data, we will use the following formula by Snedecor and Cochran 1989 to calculate the sample size (including 15% of dropout rate).

$$n = 1 + 2C \left(\frac{s}{d} \right)^2$$

s = standard deviation,

d = the difference to be detected, and

C = constant

5. Consent taking:

- a. Pregnant women with one previous Caesarean section who are indicated for IOL and eligible will be recruited in the study.
- b. Participation of the subjects is voluntary and will not affect medical services.
- c. Informed consent available in either English or Malay language (See Appendix 2) will be obtained prior to enrollment into the study.
- d. The consent will be taken by the principal investigator at time of admission in Sibu Hospital Labour Ward.

6. Subject withdrawal:

- a. Criteria:

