 - i. Subjects may withdraw voluntarily from study at any time upon their request.
 - ii. Subjects are inappropriately enrolled without fulfilling inclusion/exclusion criteria.
 - iii. Subjects develop spontaneous labour before IOL procedure is undertaken.
- b. Follow up process:
 - i. The withdrawn subjects will be managed according to local protocol under Department O&G, Sibu Hospital.
 - ii. The withdrawn subjects data will be destroyed as it will not be used for data analysis.
- c. The withdrawn subjects will be replaced with new subjects in order to meet the required sample size.

TREATMENT AND PROCEDURES

1. Treatment and medications that are permitted during the trial:
 - a. Amniotomy
 - b. Oxytocin augmentation when contractions are not optimised
 - c. Abdominal and vaginal examination to assess labour progress
 - d. Intrapartum continuous fetal heart rate monitoring
 - e. Fetal scalp sampling in the presence of non-reassuring fetal heart rate
 - f. Instrumental delivery or emergency Caesarean section if indicated

2. Both IOL methods of membrane sweeping and transcervical Foley catheter do not contain drug or medication. Thus, the risk of uterine rupture is similar to spontaneous labour in women with previous Caesarean delivery. If scar dehiscence is highly suspected during labour, standard management with recourse to emergency Caesarean section will be undertaken.

3. Treatment and medications that are not permitted during the trial:
 - a. Vaginal prostaglandin E2

ASSESSMENT OF EFFICACY

1. Primary outcome:
 - a. Overall induction to delivery interval.
2. Secondary outcomes:
 - a. Induction outcomes:
 - i. Improvement of modified Bishop score at interval of 24 hours and 48 hours after induction.
 - ii. Whether oxytocin augmentation is required.
 - b. Delivery outcomes:
 - i. Mode of delivery.
 - ii. Duration of oxytocin augmentation overall and in vaginal delivery group.
 - iii. Induction to vaginal delivery interval.

- iv. Amniotomy to vaginal delivery interval.
- v. Vaginal delivery rate within 24 hours of induction and between 24-48 hours of induction.
- c. Maternal outcomes:
 - vi. Uterine hyperstimulation (> 5 contractions per 10 minutes for at least 20 minutes or a contraction lasting at least 2 minutes with/without abnormal fetal heart rate).
 - vii. Uterine rupture.
 - viii. Post-partum haemorrhage (estimated blood loss \geq 500 ml).
 - ix. Maternal pyrexia (temperature >38.0 °C once, or 37.5 °C on two occasions 2 hours apart).

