 - i. No further membrane sweeping will be performed.
 - ii. Affected subject will be withdrawn from the study.
 - iii. No rescue medication is needed as condition is self-limiting.
 - iv. Closed monitoring of vital signs and oxygen saturation for 24 hours.
 - c. Cervical tear
 - i. Examination under anaesthesia will be performed immediately.
 - ii. Cervical repair will be performed.
 - iii. Subject will be followed up till 42 days post-delivery (completion of puerperal period).
 - d. Uterine rupture
 - i. Emergency laparotomy will be performed immediately.
 - ii. Depend on the severity of uterine rupture, uterine repair or hysterectomy may be warranted.

- iii. Subject will be followed up till 42 days post-delivery (completion of puerperal period).
 - e. Maternal sepsis
 - i. Blood culture and high vaginal swab for culture will be taken.
 - ii. Broad spectrum antibiotics will be started as rescue medication.
 - iii. Unstable subjects will be nursed in intensive care unit.
 - iv. Subject will be followed up till 42 days post-delivery (completion of puerperal period).
5. Compensation of adverse events
- a. In the event of a bodily injury or illness directly resulting from the membrane sweeping or transcervical Foley catheter insertion, the department will pay for reasonable and necessary treatment.
 - b. The department is not responsible for medical expenses due to pre-existing medical conditions, any underlying diseases, any ongoing treatment process, subjects' negligence or willful misconduct, the negligence or willful misconduct of the investigators or the study site or any third parties.

STATISTICS

1. All results will be analysed using the Statistical Package for Social Sciences for Windows (SPSS for Windows).
2. Normality of numerical data (Bishop score, induction to delivery interval, induction to vaginal delivery interval, amniotomy to vaginal delivery interval, duration of oxytocin augmentation, duration of hospitalisation, APGAR score at 5 minutes, cord pH, neonatal birth weight) will be assessed using Kolmogorov-Smirnov analysis. Independent T-test (data with normal distribution) or Mann-Whitney U test (if data not normally distributed) will be used to compare these outcomes between the group of membrane sweeping and group of transcervical Foley catheter.
3. Chi-square test will be used to compare:

- a. The requirement of oxytocin augmentation following induction between the group of membrane sweeping and group of transcervical Foley catheter.

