- b. The following delivery outcomes between the group of membrane sweeping and group of transcervical Foley catheter.
 - i. Mode of delivery.
 - ii. Vaginal delivery within 24 hours of induction.
 - iii. Vaginal delivery within 24-48 hours of induction.
 - iv. The maternal outcomes (uterine hyperstimulation, uterine rupture, post-partum haemorrhage, maternal pyrexia) between the group of membrane sweeping and group of transcervical Foley catheter.

If there is at least one expected value of < 5 , Yates correction will be done.

If sample size is less than 20 or (>40 but at least one expected value <5), Fisher test instead of Chi-square test will be used.

4. Statistical significance is defined as p value < 0.05 .

CONFIDENTIALITY AND SECURITY OF SOURCE DOCUMENTS AND STUDY DATA

1. All of the subjects' information obtained in this study will be kept and handled in a confidential manner. When publishing or presenting the study results, subjects' identity will not be revealed without their expressed consent.
2. Data from the study will be archived and may be transmitted outside the country for the purpose of analysis, but subjects' identity will not be revealed at any time.
3. Following the trial, only the principal and co/sub investigators, and regulatory authorities but not the subjects have access to study data and findings.
4. Storage and archival of medical records and study data:
 - a. Medical records will be kept in the hospital record office as following hospital policy. The investigators will only keep the study data.

- b. Documents and other study materials can be accessed by staff restricted to the investigators and regulatory authorities.
- c. All data and documents or study materials will be made available whenever it is requested by relevant authorities, in the presence of investigator.
- d. Duration of study data storage will be 5 years after completion of study. Study data will be destroyed after period of storage.

FINANCE AND INSURANCE

1. This study is self-funded by Department of O&G, Sibug Hospital.

PUBLICATION POLICY

1. When publishing or presenting the study results, subjects' identity will not be revealed without their expressed consent in order to protect subjects' confidentiality.
2. Data from the study will be archived and may be transmitted outside the country for the purpose of analysis, but subjects' identity will not be revealed at any time.

INVOLVEMENT OF VULNERABLE SUBJECTS

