1. This study does not involve vulnerable subjects.

RESULTS (Dummy tables)**Table 1: Demographic characteristics**

Characteristics	Membrane sweeping	Transcervical Foley catheter	p-value
Age, years			
Parity			
Gestational age			
Ethnicity, n (%)			
Iban			
Melanau			
Bidayuh			
Malay			
Chinese			
Indian			
Others			
Foreigner			
Body mass index, kg/m ²			
Previous Caesarean section			
Tested scar			
Untested scar			
Indication of induction of labour			
Postdate			
Fetal growth restriction			
Hypertension			
Diabetes			
Others			

Table 2: Induction outcomes in two groups

Outcomes	Membrane sweeping	Transcervical Foley catheter	p-value
Bishop score at start of induction			
Bishop score after 24 hours of induction			
Bishop score after 48 hours of induction			
Change in Bishop score			
Oxytocin required			

Table 3: Delivery outcomes and maternal complications in two group

Outcomes	Membrane sweeping	Transcervical Foley catheter	p-value
Mode of delivery			
Vaginal			
Caesarean section			
Overall			
Induction to delivery interval			
Oxytocin augmentation duration			
Vaginal delivery			
Induction to delivery interval			
Amniotomy to delivery interval			
Oxytocin augmentation duration			

Within 24 hours of induction

Between 24-48 hours of induction

Indication for Caesarean section

Poor progress

Failed induction

Acute fetal distress

Suspected scar dehiscence

Others

Maternal complications

Uterine rupture

Uterine hyperstimulation

Post-partum haemorrhage

Maternal pyrexia

Duration of hospitalisation

Table 4: Neonatal outcomes in two groups

Outcomes	Membrane sweeping	Transcervical Foley catheter	p-value
APGAR score at 5 minutes			
Cord pH			
Birth weight			

[figure not shown]
REFERENCES

2. National Institute for Health and Clinical Excellence. *Inducing Labour*. NICE CG70. London: NICE; 2008.

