32. Julious SA. Sample size of 12 per group rule of thumb for a pilot study. *Pharm Stat*. 2005;4(4):287-91.

Appendix 1

Study Procedure Flow Chart

Appendix 3

DEPARTMENT OF O&G, SIBU HOSPITAL, SARAWAK

DATA COLLECTION FORM

**MEMBRANE SWEEPING VERSUS TRANSCERVICAL FOLEY CATHETER
FOR INDUCTION OF LABOUR IN WOMEN WITH PREVIOUS
CAESAREAN DELIVERY**

Patient ID :

Name : **Date/time of admission:**

IC Number : **Date/time of discharge :**

MRN :

Age :

Ethnicity : Iban Melanau Bidayuh Malay
 Chinese Indian Other Foreigner

ALLOCATED GROUP: (PLEASE TICK)

MEMBRANE SWEEPING

TRANSCERVICAL FOLEY CATHETER

SECTION A: DEMOGRAPHIC INFORMATION

Gravida / Parity:/..... Gestational age at induction of labour: weeks days

EDD/REDD:

Height (m):

Weight (kg): (at booking) (at delivery)

BMI (kg/m²):

Previous Caesarean section: *(please tick)*

a) Untested scar

If untested scar, any previous vaginal delivery?

Yes

No

b) Tested scar

Indication of induction of labour: *(please tick)*

a) Postdate

b) Fetal growth restriction

c) Hypertension

d) Diabetes

e) Other

Please specify:

SECTION B: INDUCTION OUTCOMES ***Modified Bishop score is used in this study*

Modified Bishop score:

a) At the start of induction

b) When Foley catheter dislodged < 24 hours

a) After 24 hours of induction

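### The primary interval is compared without baseline adjustment: the test is valid, but it gives up precision that one extra form field and a pre-specified model could recover

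*Combined protocol and SAP*

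**What the plan says.** The primary outcome (Assessment of Efficacy, item 1) is "Overall induction to delivery interval". Statistics, item 2 assesses normality with a Kolmogorov-Smirnov test and then states: "Independent T-test (data with normal distribution) or Mann-Whitney U test (if data not normally distributed) will be used to compare these outcomes". Item 4 adds: "Statistical significance is defined as p value < 0.05". No regression model, stratified test or adjusted sensitivity analysis appears anywhere.

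Allocation (Trial Design, study procedure, item f) is 1:1 in blocks of 6, with no stratification factor named.

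The baseline information available is as follows.

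- **Bishop score.** Eligibility requires "reassuring fetal status and modified Bishop score ≤ 6". The form's only baseline entry (Appendix 3, Section B) is "a) At the start of induction".
- **Parity and scar status.** Both are on the form for each woman (Appendix 3, Section A).
- **Previous vaginal birth.** The form asks about it directly only under an untested scar: "If untested scar, any previous vaginal delivery".

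Parity and scar status appear in "Table 1: Demographic characteristics", and starting Bishop score in Table 2, each with a p-value column. Starting Bishop score is also the reference for a secondary outcome, the improvement in score at 24 and 48 hours. None of these variables is used in the comparison of the primary interval.

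**The concern.** Baseline prognosis is handled neither in the allocation nor in the primary analysis. The protocol itself gives reason to expect starting ripeness to matter. A score of 8 or more is described as ripe, while women may enter at any score up to 6. A woman entering at 6 is 2 points short of that mark; a woman entering at 0 is 8 points short. Under the study procedure, a cervix that does not permit amniotomy at 24 hours leads to another day before reassessment. Starting ripeness can therefore feed directly into the primary outcome in steps of about a day. For previous vaginal birth, the documents show only that the investigators chose to ask about it.

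Two things are at stake. Variation that baseline values could explain stays in the error term and costs power. And when the arms happen to differ at baseline, the unadjusted estimate carries that difference with it. The p-values in Tables 1 and 2 do not help with either: they test a hypothesis that randomisation already makes true, and they correct nothing.

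**Working it through.** **Inputs from the plan.** The sample-size text (Selection and Withdrawal of Subjects, item 4) reads: "With α at 0.05 and power at 0.8, the final sample size will be calculated". The formula is n = 1 + 2C(s/d)² per arm, with 15% dropout. An interim at 24 women (12 per arm) is to supply the inputs. No values of s, d or final n are given, so there is no planned figure to reproduce.

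**Assumptions.** Two-sided α; d/s = 0.5 as the worked case; R² (the share of outcome variance explained by the two covariates) from 0 to 0.30.

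**Step 1: sample size.** C = (1.960 + 0.842)² ≈ 7.849. At d/s = 0.5, n = 1 + 2 × 7.849 / 0.25 = 63.8, so 64 per arm. With dropout, 64 / 0.85 = 75.3, so 76.

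**Step 2: power at 64 per arm.** Adjustment multiplies the residual variance by (1 − R²). In large samples, power ≈ Φ(0.5 / √(2(1 − R²)/64) − 1.960).

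- R² = 0: 0.5 / 0.1768 = 2.828; 2.828 − 1.960 = 0.868; power 0.807 (0.80 by the noncentral t).
- R² = 0.20: 2.828 / √0.80 = 3.162; 3.162 − 1.960 = 1.202; power 0.885.

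Estimating two covariates has a cost. With N women in total, the variance is also multiplied by (N − 3)/(N − 5), here 125/123 = 1.016. The third column below includes this and uses the noncentral t with 124 degrees of freedom. The fourth is a simulation of 10,000 trials per setting with normal errors.

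| R² | Large-sample | With covariate cost | Simulated, adjusted (unadjusted) | n per arm for the same power |
|---|---|---|---|---|
| 0 | 0.807 | 0.795 | 0.794 (0.799) | 64 |
| 0.05 | 0.827 | 0.815 | not run | 61 |
| 0.10 | 0.846 | 0.835 | 0.828 (0.793) | 58 |
| 0.20 | 0.885 | 0.875 | 0.873 (0.799) | 52 |
| 0.30 | 0.922 | 0.914 | 0.915 (0.804) | 45 |

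The last column is 1 + 2C(1 − R²)/0.25, rounded up. For other assumed values at R² = 0.20, n per arm falls from 176 to 141 (d/s = 0.3) and from 26 to 21 (d/s = 0.8).

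**Step 3: validity.** With no true difference, simulated type I error was between 0.046 and 0.054 for both analyses in every setting, at 12 and at 64 per arm.

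**Step 4: when adjustment stops paying.** It gains precision only if (1 − R²)(N − 3)/(N − 5) < 1, that is R² > 2/(N − 3). At N = 128 this is 2/125 = 0.016. At N = 24 it is 2/21 = 0.095.

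**Step 5: chance imbalance.** The SD of the difference in baseline means is √(2/n) baseline SDs, or 0.177 at 64 per arm. The chance of a difference above 0.25 SD is 2(1 − Φ(0.25/0.177)) = 0.16. Such a difference shifts the unadjusted estimate by 0.25√R² outcome SDs: 0.08 at R² = 0.10 and 0.11 at R² = 0.20, against an assumed target of 0.5.

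**The case against.** The strongest reply is that nothing is broken. A two-sample test after 1:1 randomisation is valid, and the sample-size formula is for the same unadjusted comparison, so design and analysis agree and the stated power of 0.8 is not lost. Chance imbalance is already part of the unadjusted standard error. All of this stands. A reader might infer that the unadjusted result would be biased or that its error rate would be inflated; Step 3 shows otherwise.

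Four further cautions stand.

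- **The gain is assumed.** No R² is given, and the limit of 6 on the Bishop score narrows its range and may weaken its prognostic value. In smaller trials a weak R² buys little: at 26 per arm (d/s = 0.8), R² = 0.05 moves power only from 0.807 to 0.811.
- **Previous vaginal birth is not recorded directly for every woman.** A reader might take it so, or might equate a tested scar with a vaginal birth. The question is asked only under an untested scar, and the documents never define a tested scar.
- **The change is not entirely free of new data.** Consent is taken at admission, the envelope is opened once consent is signed, and induction follows the next morning in an unblinded trial. On that sequence the form's only baseline score is taken after allocation is known.
- **The interim is a different case.** At 12 per arm the chance of a baseline difference above 0.25 SD is 0.54, and a reader might carry that over to the final result. The 24-woman stage serves to set the sample size and is not the final comparison.

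These points limit the claim. They do not remove the case for pre-specifying an adjusted analysis, whose cost when R² = 0 was 0.005 of power in the simulation (0.794 against 0.799).

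**Conclusion.** The point holds as a cheap gain in precision and not as the correction of an error. At an assumed 64 per arm and d/s = 0.5, power rises from about 0.80 to about 0.82, 0.84, 0.88 or 0.91–0.92 for R² of 0.05, 0.10, 0.20 or 0.30, and the loss is negligible if R² is 0. Expressed as sample size, 61, 58, 52 or 45 per arm would do in place of 64. These figures rest on assumed values of d/s and R², two-sided testing and roughly normal errors. The documents supply none of the quantities needed to say which row applies. The benefit belongs to the full trial; at 24 women, adjustment could cost precision if R² is below about 0.095.

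**What to change.** In Statistics, item 2, before any outcome data are compared by arm:

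1. Make the primary analysis of the full trial a linear regression of the interval on arm, baseline modified Bishop score (continuous) and any previous vaginal birth.
2. State in advance how skew is handled, since the plan already anticipates non-normal data: either a log transformation, with the effect reported as a ratio, or robust standard errors, with the effect kept in hours.
3. Report the adjusted difference with its 95% CI, and keep the unadjusted test as a sensitivity analysis.
4. Use the Bishop score assessed for eligibility before the envelope is opened, and add one field to Appendix 3 to record it.
5. Define previous vaginal birth for all women from recorded parity, given exactly one previous Caesarean. Cross-check it against scar status and the question asked for an untested scar.

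The cost is a few lines of analysis text, one form field and two estimated covariates. SPSS fits the model. Removing the baseline p-values from Tables 1 and 2 is an optional reporting change that does not affect the result.

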32. Julious SA. Sample size of 12 per group rule of thumb for a pilot study. *Pharm Stat*. 2005;4(4):287-91.

Appendix 1

Study Procedure Flow Chart

Appendix 3

DEPARTMENT OF O&G, SIBU HOSPITAL, SARAWAK

DATA COLLECTION FORM

**MEMBRANE SWEEPING VERSUS TRANSCERVICAL FOLEY CATHETER
FOR INDUCTION OF LABOUR IN WOMEN WITH PREVIOUS
CAESAREAN DELIVERY**

Patient ID :

Name : **Date/time of admission:**

IC Number : **Date/time of discharge :**

MRN :

Age :

Ethnicity : Iban Melanau Bidayuh Malay
 Chinese Indian Other Foreigner

ALLOCATED GROUP: (PLEASE TICK)

MEMBRANE SWEEPING

TRANSCERVICAL FOLEY CATHETER

SECTION A: DEMOGRAPHIC INFORMATION

Gravida / Parity:/..... Gestational age at induction of labour: weeks days

EDD/REDD:

Height (m):

Weight (kg): (at booking) (at delivery)

BMI (kg/m²):

Previous Caesarean section: *(please tick)*

a) Untested scar

If untested scar, any previous vaginal delivery?

Yes

No

b) Tested scar

Indication of induction of labour: *(please tick)*

a) Postdate

b) Fetal growth restriction

c) Hypertension

d) Diabetes

e) Other

Please specify:

SECTION B: INDUCTION OUTCOMES ***Modified Bishop score is used in this study*

Modified Bishop score:

a) At the start of induction

b) When Foley catheter dislodged < 24 hours

a) After 24 hours of induction

b) After 48 hours of induction

(only applicable to Foley group)

Achieved favourable Bishop (≥ 8) score: *(please tick)*

Yes

No

(if yes, proceed to sub-question;

if no, proceed to next question)

a) Interval to achieve favourable Bishop score

_____ (hours)

Achieved cervix allowing amniotomy: *(please tick)*

Yes

No

(if yes, proceed to sub-question;

if no, proceed to next section)

a) Bishop score at that time

b) Os dilatation at that time

_____ (cm)

c) Cervical length at that time

_____ (cm)

SECTION C: DELIVERY OUTCOMES

Oxytocin required during delivery (*please tick*) Yes No

Mode of delivery: (*please tick*)

- Vaginally Within 24 / 24-48 / > 48 hours of induction (*please circle*)
- Instrumentation Vacuum / forceps (*please circle*)
Indication: _____
- Caesarean section Indication: _____

Durations (regardless of final mode of delivery):

- a) Induction to delivery _____ (hours)
- b) Oxytocin augmentation _____ (minutes)

Durations (only for vaginal delivery including instrumental delivery):

- a) Induction to vaginal delivery _____ (hours)
- b) Amniotomy to vaginal delivery _____ (hours)
- c) Oxytocin augmentation _____ (minutes)

Estimated blood loss (EBL): ml

If EBL > 500ml, please mention cause: (*please tick*)

- a) Uterine atony
- b) Perineal trauma
- c) Retained placenta
- d) Coagulopathy
- e) Others *Please specify:*

Maternal complications: (*please tick*)

- a) Uterine rupture Yes No
- b) Uterine hyperstimulation Yes No
- c) Post-partum haemorrhage Yes No
- d) Maternal pyrexia Yes No

Neonatal outcomes:

- a) APGAR score at 5 minutes _____ To: NICU / SCN / mother (*please circle*)
- b) Cord pH _____
- c) Birth weight _____

SECTION D: MATERNAL SATISFACTION

If you had to repeat it all over again, would you take part in the study? (*please tick*)

Yes

No

If no, please provide reason(s). _____

Notes:

Uterine hyperstimulation : > 5 contractions per 10 minutes for at least 20 minutes or a contraction lasting at least 2 minutes with/without abnormal fetal heart rate

Post-partum haemorrhage : Estimated blood loss \geq 500 ml

Maternal pyrexia : Temperature >38.0 °C once, or 37.5 °C on two occasions 2 hours apart
